13.8.2. Safety Analyses

The All Treated Subjects Population will be used for the analysis of safety data. All serially collected safety endpoints (e.g. laboratory tests, vital signs, electrocardiogram [ECGs]) will be summarized according to the scheduled, nominal visit at which they were collected and across all on-treatment time points using a “worst-case” analysis. Complete details of the safety analyses will be provided in the Reporting and Analysis Plan (RAP).

Safety endpoints are described in Section 2. Complete details of the safety analyses will be provided in the RAP.

A listing by subject including treatment administered, and compliance, will be generated with dates and times of treatment administered. The number of subjects exposed to study drug will be tabulated for Part 1 (for each dose cohort) and Part 2.

All relevant safety data will be listed and summarized according to IDSL standards. The reporting and analysis plan will list the IDSL templates for the displays. Adverse events will be coded and grouped by system organ class (SOC) and preferred (coded) term (PT) using the Medical Dictionary for Regulatory Activities (MedDRA) system for adverse event coding. AEs will be graded according to the National Cancer Institute Common Terminology Criteria for Adverse Events (NCI CTCAE) Version 4.03. Adverse events will be summarized by maximum toxicity grade for each initial dose level. All AEs will be listed. A summary of the number and percent of subjects reporting each AE at least once will be produced for all AEs, for drug-related AEs and for SAEs for Part 1 (for each dose cohort) and Part 2. A listing of those AEs identified as dose-limiting toxicities will also be produced for each dose cohort for Part 1. A listing showing the relationship of AE

verbatim text to group terms and body systems will also be produced. A listing of withdrawals due to AEs will be provided. Deaths and SAEs will be listed should they occur.

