**Table 1 Changes to Protocol Defined Analysis Plan**

Protocol	Reporting & Analysis Plan	
Statistical Analysis Plan	Statistical Analysis Plan	Rationale for Changes

 
Interim Analysis and CSR for Part 2
 
	
 
No Statistical Analysis for Part 2
 
	
 
Part 2 was not implemented
 

 
Full CSR
 
	
 
Abbreviated CSR
 
	
 
Study terminated
 

 
Pharmacokinetic Analysis of ATRA for Part 1
 
	
 
Pharmacokinetic Analysis of ATRA for Part 1 will not be performed
 
	
 
ATRA samples not provided to the analytical lab with adequate protection to light resulting in a very limited number of analysable samples which concentration are listed.
 

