Summaries of worst case grade increase from baseline grade will be provided for all the lab tests that are gradable by CTCAE v4.0. These summaries will display the number and percentage of subjects with a maximum post-baseline grade increasing from their baseline grade. Any increase in grade from baseline will be summarized along with any increase to a maximum grade of 3 and any increase to a maximum grade of 4. Missing baseline grade will be assumed as grade 0. For laboratory tests that are graded for both

low and high values, summaries will be done separately and labeled by direction, e.g., sodium will be summarized as hyponatremia and hypernatremia.

For lab tests that are not gradable by CTCAE v4.0, summaries of worst case changes from baseline with respect to normal range will be generated. Decreases to low, changes to normal or no changes from baseline, and increases to high will be summarized for the worst case post-baseline. If a subject has a decrease to low and an increase to high during the post-baseline time period, then the subject is counted in both the “Decrease to Low” categories and the “Increase to High” categories.

A supporting listing of all chemistry and haematology laboratory data will be provided.

Unless otherwise specified, the denominator in percentage calculation at each scheduled visit will be based on the number of subjects with non-missing value at each particular visit.

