### **7.3.1. Liver Function Analyses**

Summaries of hepatobiliary laboratory events including possible Hy’s law cases will be provided in addition to what has been described above.

Possible Hy’s law cases are defined as any elevated (ALT>3×ULN **and** total bilirubin ≥2×ULN (with direct bilirubin ≥35% of total bilirubin, if direct bilirubin is measured)) **OR** (ALT ≥3 times ULN **and** INR >1.5, if INR is measured).

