### **ECG**

A summary of the number and percentage of subjects who had normal and abnormal (clinically significant and not clinically significant) ECG findings will be displayed by scheduled visits as well as for the worst case post-baseline. The summaries for the QTc will use the collected value based on QTcB and QTcF.

The QTcB and QTcF values will be rounded to the integer and the values will be categorized into the following ranges: Grade 0 (<450), Grade 1 (450-480), Grade 2 (481-500), and Grade 3 (≥501). Summaries of grades will display the number and percentage of subjects by grade in the worst case post-baseline. Similarly, grade changes relative to baseline grade will also be generated.

Listings of abnormal ECG findings and a listing of ECG values will be provided.

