**ECOG Performance Status**

A summary of change from baseline in ECOG performance status by scheduled visits will be performed. Summaries will use frequency and percentage of subjects at each planned assessment time, best and worst-case post baseline.

A supporting listing will also be provided.

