### 11.5.2. Reporting Standards

General	

 
The current GSK Integrated Data Standards Library (IDSL) will be applied for reporting, unless otherwise stated (IDSL Standards Location: https://spope.gsk.com/sites/IDSLLibrary/SitePages/Home.aspx):             
 
4.03 to 4.23: General Principles
 
5.01 to 5.08: Principles Related to Data Listings
 
6.01 to 6.11: Principles Related to Summary Tables
 
7.01 to 7.13: Principles Related to Graphics
 
 
 
	
Formats	

 
GSK IDSL Statistical Principles (5.03 & 6.06.3) for decimal places (DP's) will be adopted for reporting of data based on the raw data collected, unless otherwise stated.
 
Numeric data will be reported at the precision collected on the eCRF.
 
The reported precision from non eCRF sources will follow the IDSL statistical principles but may be adjusted to a clinically interpretable number of DP's.
 
	
Planned and Actual Time	

 
Reporting for tables, figures and formal statistical analyses:             
 
Planned time relative to dosing will be used in figures, summaries, statistical analyses and calculation of any derived parameters, unless otherwise stated.
 
The impact of any major deviation from the planned assessment times and/or scheduled visit days on the analyses and interpretation of the results will be assessed as appropriate.
 
 
 
Reporting for Data Listings:             
 
Planned and actual time relative to study drug dosing will be shown in listings (Refer to IDSL Statistical Principle 5.05.1).
 
Unscheduled or unplanned readings will be presented within the subject's listings.
 
Visits outside the protocol defined time-windows (i.e. recorded as protocol deviations) will be included in listings but omitted from figures, summaries and statistical analyses.
 
 
 
	
Unscheduled Visits	

 
Unscheduled visits will not be included in summary tables and figures.
 
	

 
All unscheduled visits will be included in listings
 
	
Descriptive Summary Statistics	

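### The SAP's exclusion of unscheduled visits from summary tables has no stated exception for worst-case safety tables, although the protocol asks for a worst case over all on-treatment time points

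*SAP*

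**What the plan says.** Protocol Section 13.8.2 covers serially collected safety endpoints such as laboratory tests, vital signs and ECGs. They are to be "summarized according to the scheduled, nominal visit at which they were collected and across all on-treatment time points", the second of these as a worst-case analysis. The section leaves complete details to the reporting and analysis plan. Section 13.8 requires departures from the protocol's analysis plan to be documented in that plan and in the study report.

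SAP Section 11.5.2 has two exclusion rules:

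- On unscheduled visits: "Unscheduled visits will not be included in summary tables and figures". They appear in listings.
- On timing: "Visits outside the protocol defined time-windows (i.e. recorded as protocol deviations) will be included in listings but omitted from figures, summaries and statistical analyses". This bullet sits under the sub-heading on data listings.

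The SAP keeps several maximum or worst-case displays:

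- Section 7.3, laboratory grades: "These summaries will display the number and percentage of subjects with a maximum post-baseline grade increasing from their baseline grade".
- Section 7.3.1: "Summaries of hepatobiliary laboratory events including possible" Hy's law cases.
- Section 7.4, ECG: "ECG findings will be displayed by scheduled visits as well as for the worst case post-baseline".
- Section 7.4, ECOG: "Summaries will use frequency and percentage of subjects at each planned assessment time, best and worst-case post baseline".

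SAP Table 1, "Changes to Protocol Defined Analysis Plan", has three rows: no Part 2 analysis, an abbreviated report, and no PK analysis of ATRA.

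**The concern.** A worst-case table is meant to catch the most extreme value wherever it falls. In this study, extra blood draws are often prompted by an abnormal result, so an extreme value may well come from an unscheduled visit. If the rule in Section 11.5.2 is programmed as written, those values do not enter the maximum-grade tables or the count of possible Hy's law cases, and some subjects may be shown with a milder worst grade than they had.

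Changes in laboratory values are part of the Part 1 primary endpoint, and the protocol's risk assessment names thrombocytopenia as the drug's primary toxicity. If the exclusion does reach the worst-case tables, it is also a departure from Protocol Section 13.8.2 that SAP Table 1 does not record.

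**Working it through.** No figure in the plan bears on this, so the check is a comparison of texts.

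**1. Is the exclusion qualified?** Neighbouring entries in SAP Section 11.5.2, on reporting standards, decimal places and planned time, allow for exceptions stated elsewhere. The unscheduled-visit rule carries no such wording.

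**2. Does another part of the SAP supply an exception?**

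| Place in SAP | What it contributes | Unscheduled values mentioned? |
|---|---|---|
| 7.3, laboratory grades | Maximum post-baseline grade | No |
| 7.3.1, liver function | Possible Hy's law cases defined by laboratory values | No |
| 7.4, ECG and ECOG | Worst case, set beside by-visit results | No, but the contrast is suggestive |
| 11.6.1, multiple measurements | High and low values at any post-baseline visit are both counted | No |
| 11.7.1, withdrawals | Available planned data from withdrawn subjects enter summaries | No; the word planned leans towards exclusion |
| 11.10.6, notes to Tables 3.7 and 3.9 | Ask for the worst case to be included | No |

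No express exception is found.

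**3. Is a departure declared?** None of the three rows of SAP Table 1 concerns visits or worst-case derivations.

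**4. Will such values arise?** The protocol foresees them:

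- Section 4.8.3 allows more frequent monitoring while dosing continues through Grade 1 to 3 thrombocytopenia.
- Footnote 4 to Table 3 in Section 7.1 refers to an unscheduled blood count.
- Footnote 16 to the same table allows twice-weekly counts to go on beyond the planned schedule.
- Section 7.3.7 asks for significantly abnormal tests to be repeated until they return to normal or baseline.

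**5. Which way does the rule act?** For one subject and one test, the maximum grade over scheduled visits alone is equal to or lower than the maximum over all visits in the same period, because the first set lies within the second. The same holds for whether a subject ever meets the Hy's law definition. This does not carry over in full to two other kinds of table:

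- *Increase from baseline.* Section 5.2 takes the latest value on or before the first dose date. If unscheduled pre-dose values are also dropped, the baseline can change, and Section 7.3 treats a missing baseline grade as 0. The net direction is then unknown.
- *QTc.* Protocol Section 4.7.2 averages repeat ECGs with the one that triggered them, and SAP Section 11.6.1 averages multiple measurements at one time point. Adding repeats could therefore move the value either way.

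**The case against.** The best reply is that no conflict is intended. Section 7.4 sets scheduled visits against worst case for ECG, and planned times against best and worst case for ECOG. A programmer could reasonably conclude that Section 11.5.2 governs only the by-visit half. Protocol Section 13.8.2 does not mention unscheduled samples, and elsewhere the protocol speaks of planned time points for safety assessments. Many of the tables follow company display templates that neither document reproduces, and part of the mock shells in SAP Appendix 11 was not available. Any of these could settle the question in favour of inclusion. This stands as a reason not to say that the SAP definitely excludes the values. It does not remove the gap, because the only explicit rule points the other way.

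The harm is also limited. The study was terminated, the analysis is descriptive, and every value is listed. Dose escalation rests on dose-limiting toxicities through the escalation models, not on these tables. Laboratory results that led to an intervention are recorded as adverse events. That backstop is only partial: under Protocol Section 8.3, clinically significant findings associated with the underlying leukaemia are not reported as adverse events unless more severe than expected. Listings show values but do not count subjects.

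A reader might try to size the effect by comparing the four weeks of weekly liver monitoring in Protocol Section 4.7.1 with the chemistry row of Table 3. The documents do not support that count. The SAP rule concerns visits, and Table 3 already has weekly scheduled blood draws in weeks 4 to 7 and at week 8. An extra chemistry test taken then need not belong to an unscheduled visit.

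A reader might also take the timing bullet to discard everything outside the windows in Protocol Section 7 (±1 day in the first 4 weeks, ±3 days later). As worded, it is tied to visits recorded as protocol deviations.

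**Conclusion.** The point holds as a minor one. The SAP contains an unqualified exclusion which, followed literally, conflicts with the worst-case analysis in Protocol Section 13.8.2; no visible SAP text lifts it, and SAP Table 1 records no departure. The likely consequence is that some subjects' worst laboratory grades, and possibly some Hy's law cases, are understated in the summary tables. The size cannot be computed from the documents.

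This rests on two assumptions: that the rule is applied as written, and that extra samples are recorded as unscheduled visits. It does not show that the sponsor means to exclude these values, that every safety table would look more favourable, or that dose decisions were affected.

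**What to change.** In SAP Section 11.5.2, replace the two exclusion rules with wording such as: *Unscheduled and out-of-window assessments are excluded from by-visit summaries only; all post-baseline assessments, scheduled or not, are used in maximum and worst-case tables, and unscheduled pre-dose values remain eligible as baseline under Section 5.2.*

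The worst-case tables should not be narrowed to on-treatment values in the process. SAP Section 11.4.1 ends the on-treatment phase at the treatment stop date, while the protocol allows the end-of-treatment visit up to 14 days after the last dose and requires liver follow-up after stopping. Such a limit would remove values that the SAP's post-baseline tables now take in. Since the post-baseline period is then wider than the protocol's on-treatment period, note that in SAP Table 1.

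If the exclusion is meant to apply to worst-case tables, add a row to SAP Table 1 with the reason.

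The cost is a sentence or two and, at most, a changed filter in the table programs. The data are already collected and listed. Some reported worst grades may become higher.

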### 11.5.3. Reporting Standards for Pharmacokinetic

Pharmacokinetic Concentration Data	
PC Windows Non-Linear (WNL) File	PC WNL file (CSV format) for the non-compartmental analysis by Clinical Pharmacology Modelling and Simulation function will be created according to [Insert document name]. Note: Concentration values will be imputed as per GUI_51487
Descriptive Summary Statistics, Graphical Displays and Listings	Refer to IDSL PK Display Standards. Refer to IDSL Statistical Principle 6.06.1. Note: Concentration values will be imputed as per GUI_51487 for descriptive summary statistics/analysis and summarized graphical displays only.
Pharmacokinetic Parameter Data	
Is NQ impacted PK Parameters Rule Being Followed	Yes, refer to [Standards for Handling NQ Impacted PK Parameters].
Descriptive Summary Statistics, Graphical Displays and Listings	Refer to IDSL PK Display Standards. Refer to GUI_51487

## 11.6. Appendix 6: Derived and Transformed Data

### 11.6.1. General

Multiple Measurements at One Analysis Time Point

 
• Mean of the measurements will be calculated and used in any derivation of summary statistics but if listed, all data will be presented.
 
• If there are two values within a time window the value closest to the target day for that window will be used. If values are the same distance from the target, then the mean will be taken.
 
• Participants having both High and Low values for Normal Ranges at any post-baseline visit for safety parameters will be counted in both the High and Low categories of “Any visit post-baseline” row of related summary tables. This will also be applicable to relevant Potential Clinical Importance summary tables.
 

Study Day

 
• Calculated as the number of days from First Dose Date:             
 
• Ref Date = Missing → Study Day = Missing
 
• Ref Date < First Dose Date → Study Day = Ref Date – First Dose Date
 
• Ref Date ≥ First Dose Date → Study Day = Ref Date – (First Dose Date) + 1
 
 
 

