**11.3. Appendix 3: Assessment Windows**

No assessment windows will be applied.

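### The SAP's rule of averaging repeat measurements has no exception for toxicity grades, so it conflicts with the maximum-grade tables and could understate Grade 4 counts

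*SAP*

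**What the plan says.** Four sets of text bear on the point.

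- **Repeats at one time point.** SAP 11.6.1 states: "Mean of the measurements will be calculated and used in any derivation of summary statistics". It adds, for listings, "but if listed, all data will be presented". A second bullet gives a different rule: "If there are two values within a time window the value closest to the target day for that window will be used", with the mean only for ties. A third bullet counts a subject who has both high and low values in both categories.
- **Worst-case laboratory tables.** SAP 7.3, after its Table 2, says: "Summaries of worst case grade increase from baseline grade will be provided for all the lab tests that are gradable" by CTCAE. It defines them by the "number and percentage of subjects with a maximum post-baseline grade increasing from their baseline grade", and counts separately "any increase to a maximum grade of 4". The programming note for Table 3.9 (haematology) asks for the worst case. Protocol 13.8.2 wants serial safety endpoints summarised by nominal visit and also "across all on-treatment time points using a" worst-case approach.
- **Unscheduled visits.** SAP 11.5.2 keeps them in listings and leaves them out of summary tables and figures.
- **Windows.** SAP 11.3: "No assessment windows will be applied".

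**The concern.** A mean and a maximum answer different questions. The mean at a time point suits a by-visit summary of a continuous measure. A worst-case toxicity table needs the most extreme single value in the direction of harm. SAP 11.6.1 makes no such distinction, and neither document says whether a value is graded before or after averaging. Two programmers working from this SAP could therefore produce different Grade 4 counts from the same data.

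The haematology table is where this matters most. Protocol 1.3.3 names thrombocytopenia as the dose-limiting toxicity in animals, protocol 1.3.5 reports two subjects with treatment-related Grade 4 thrombocytopenia, and SAP 7.2 lists thrombocytopenia and neutropenia as events of special interest. Any error from averaging a low count with a higher one runs in one direction, towards less apparent toxicity. The exclusion of unscheduled visits works the same way when the lowest count was found between planned visits.

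**Working it through.** The plan states no figure on this point, so there is none to reproduce. The check is whether the rule reaches the grade tables, and what it does if it does.

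**Inputs.** Grade 4 platelets: below 25,000/mm³ (protocol 4.8.3). Dose-level sizes at 20 November 2015: 1, 2, 7 and 1 subjects (protocol 1.3.5). The platelet values below are illustrative assumptions; the documents give no subject-level counts.

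**Step 1: does the rule reach grade counts?** SAP 11.5.2 lists frequency and percentage among its descriptive summary statistics for categorical data. Grade counts are therefore summary statistics in the SAP's own terms, and a literal reading of 11.6.1 covers them. The high-and-low bullet does not help, because two low platelet counts lie in the same direction.

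**Step 2: when is Grade 4 lost at a time point?** For two values a and b with a < 25,000, the mean is (a + b)/2. It stays Grade 4 only if (a + b)/2 < 25,000, that is a + b < 50,000. Grade 4 is lost when b ≥ 50,000 − a.

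| First value a | Second value at which Grade 4 is lost |
|---|---|
| 5,000 | 45,000 or more |
| 10,000 | 40,000 or more |
| 20,000 | 30,000 or more |
| 24,000 | 26,000 or more |

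| Pair | Mean | Grade of the mean | Grade of the worst value |
|---|---|---|---|
| 9,000 and 45,000 | 54,000/2 = 27,000 | below Grade 4 | 4 |
| 20,000 and 31,000 | 51,000/2 = 25,500 | below Grade 4 | 4 |
| 24,000 and 26,000 | 50,000/2 = 25,000 | below Grade 4 | 4 |
| 8,000 and 30,000 | 38,000/2 = 19,000 | 4 | 4 |

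**Step 3: when is it lost for the subject?** Table 3.9 takes the maximum over visits. If the subject has one other scheduled value below 25,000, say a single 18,000, the maximum is still Grade 4. A subject already at Grade 4 at baseline cannot contribute, because the table counts increases from baseline grade.

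**Step 4: the unscheduled route.** Suppose the scheduled counts are all 30,000 and one unscheduled count is 12,000. Under SAP 11.5.2 the 12,000 does not enter the table, so the subject is not counted at Grade 4. No averaging and no second value are needed.

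**Step 5: what one subject is worth.** A lost case changes a dose column by 1/n. With the sizes above that is 1/7 = 14 percentage points for the largest group, 1/2 = 50 for the next, and 100 for a group of one. These are interim sizes, and the figures apply only if such a case occurs.

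**The case against.** The strongest reply is that SAP 7.3 is the specific rule for these tables. Defining them by maximum post-baseline grade can be read as grading every value and keeping the worst, and a general appendix bullet should not override that. This stands as far as it goes: the SAP nowhere says that averaging comes first. It leaves the conflict in place, since 11.6.1 claims every derivation and 7.3 does not exempt itself. The sponsor's display standards may settle the order, but the SAP does not say so.

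Second, a repeat recorded at an unscheduled visit is excluded, not averaged, so a scheduled Grade 4 value would survive it. That is right, and it narrows the averaging route to two values filed under the same scheduled time point. The same exclusion does harm when the Grade 4 value is itself the unscheduled one.

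Third, a reader might infer that critical counts are commonly repeated or transfused on the same day. The documents do not support that. Protocol 7.3.7 asks for significantly abnormal tests to be repeated until they recover, and protocol 4.8.3 leaves transfusion to judgement or institutional guidelines; neither gives a same-day timing or a frequency.

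Fourth, there are backstops. Blood counts are twice weekly for four weeks and then weekly for four (protocol 7.3), so another scheduled Grade 4 value may well exist. Listings show all values, and SAP 7.1 and 7.2 report adverse events by maximum grade and by special interest. These limit the loss. The adverse event route is only partial: protocol 8.3 requires an event for a result that led to an intervention, but exempts disease-related findings unless worse than expected, and cytopenias in AML may be attributed to disease.

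Fifth, the time window in 11.6.1 might mean the protocol's visit windows, which SAP 11.5.2 mentions. That is possible, but the text still sits badly with 11.3.

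Finally, Part 1 is descriptive and the report is abbreviated. That lowers the stakes, although safety remains the primary objective of Part 1.

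**Conclusion.** The point holds as a conflict between stated rules. On a literal reading of 11.6.1, same-time-point repeats totalling 50,000/mm³ or more remove a Grade 4 platelet result that SAP 7.3, Table 3.9 and protocol 13.8.2 intend to count. Table 3.9 could therefore be understated. The loss at subject level requires two values at one scheduled time point, a mean at or above 25,000, and no other scheduled Grade 4 value. The exclusion of unscheduled visits is the more direct route and needs only that the subject's sole Grade 4 value was unscheduled.

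A reader might go further and infer that the SAP orders averaging before grading, or that Grade 4 results will be erased from the report. The documents do not support either: the order is unstated, every value stays in the listings, and reported adverse events keep their grade. How often either route would operate cannot be computed from the documents. The platelet pairs are assumptions that show the mechanism and give no rate. The change is worth making because the tables are small and the correction is simple.

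**What to change.** 1. In SAP 11.6.1, limit the mean to by-visit summaries of continuous measures and to replicate ECGs. For the latter, the mean matches protocol 4.7.2, which averages triplicate QTc readings.
2. In SAP 7.3, state that every on-treatment post-baseline value, including repeats at the same time point and unscheduled values, is graded individually before the worst grade is taken. Write this as an explicit exception to the unscheduled-visit rule in 11.5.2, and repeat it in the programming note for Table 3.9 and the other worst-case displays.
3. Delete the bullet that picks the value closest to the target day, or reconcile it with 11.3.

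The cost is SAP wording and a programming note, with no new data collection. Reported Grade 3-4 laboratory rates may be slightly higher than under the literal rule.
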